3.1 Study Periods

The ARC004 study consists of 4 study periods:

- Initial Escalation - Group 1 only
- Up-dosing - Group 1 or Repeat Up-dosing for subjects switching to a daily AR101 dosing regimen (Section 3) at a study site that has not yet received approval to enroll these subjects in ARC008

- Maintenance - Group 1 and subjects switching to a daily AR101 dosing regimen and who completed Repeat Up-dosing at a study site that has not yet received approval to enroll these subjects in ARC008
- Extended Maintenance - Groups 1 and 2

3.1.1 Initial Escalation (Group 1 Only)

All Initial Escalation doses will be administered by investigational site personnel under direct observation. Eligible subjects will initiate treatment with AR101 on Day 1, starting at a dose of 0.5 mg, increasing the dose at 20 to 30 minute intervals to a maximum dose of 6 mg ([Table 1](#)). Subjects who fail to tolerate ≥ 3 mg dose on Day 1 will be considered escalation failures and will be discontinued. Subjects who tolerate ≥ 3 mg dose on Day 1 will undergo confirmatory dosing of a single 3 mg dose on Day 2. Subjects who do not tolerate this confirmatory dose will be discontinued. Subjects who tolerate this confirmatory dose will enter the Up-dosing Period.

Table 1: Initial Escalation Schedule (Group 1 Subjects Only)

Initial Escalation Schedule (Group 1 only)		
Day 1 Dose Number	AR101 Dose, mg*	Cumulative AR101 Dose, mg
1	0.5	0.5
2	1	1.5
3	1.5	3
4	3	6
5	6	12
Day 2 Dose Number	AR101 Dose, mg	Cumulative AR101 Dose, mg
1	3	3

*All mg doses shown refer to milligrams of peanut protein.

Doses will be delivered at 20 to 30 minute intervals under direct observation.

Capsules are to be opened, contents sprinkled over an age-appropriate food, and mixed thoroughly.

Day 1: Subjects who are unable to tolerate a dose of 3 mg at the end of Day 1 will be considered escalation failures. Subjects who tolerate ≥ 3 mg on Day 1 will return on Day 2 to receive a 3-mg single dose.

Day 2: Subjects with either no symptoms or mild symptoms on Day 2 at 3 mg will start daily home dosing at 3 mg on Day 3.

Subjects with moderate or severe symptoms at 3 mg on either Day 1 or Day 2 will be considered escalation failures.

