At a minimum, subjects must be observed for 1½ hours after dose administration, with vital sign measurements and assessment for signs and symptoms of allergic reaction performed every 30 minutes. Any signs or symptoms of allergic reaction will be recorded in the CRF on the appropriate Dosing Symptom/AE form.

If Day 2 dosing is completed with no symptoms detected after 1½ hours of post-dose observation, the subject may be sent home from the CRC. If the subject exhibited mild symptoms, the duration of the observation period should be a minimum of 1 hour after resolution of the symptoms. For moderate symptoms, the observation period should be extended to a minimum of 2 hours after resolution of the symptoms. For severe symptoms, the subject should be observed for a minimum of 3 hours after resolution of the symptoms, either at the CRC or an emergency facility, as appropriate.

Any subject deemed to have severe symptoms that include hypoxia, hypotension, or change in mental status (stage 3 anaphylaxis defined in [Appendix 3](#)), or who receives intensive therapy (to be determined by the investigator, but may include such interventions as IV epinephrine, intubation, or admission to an intensive care unit) for an allergic reaction at any time should be discussed with the Medical Monitor and discontinued from the study.

If dose-limiting symptoms occur on Day 2, there will be no further dosing of AR101, and the subject will be classified as an escalation failure and a nonresponder for the purpose of primary and key secondary analyses. The subject will be asked to return to the CRC 14 days following the last dose of study product to undergo an Early Discontinuation Visit ([Section 6.3.10](#)). Adverse events will be evaluated from the onset until the event is resolved or medically stable, or until 30 days after the Early Discontinuation Visit, whichever comes first.

Those subjects who tolerate the single 3 mg dose of study product on Day 2 will be dispensed a 2-week supply of study product at the 3 mg/d dose level. They will be instructed to continue daily oral dosing at home, starting the following day (Study Day 3), and to continue daily home dosing at that dose level for 2 weeks until next escalation.

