6.5.2 Assessment of the Tolerability of an Individual Dose of Study Product

Determination of the tolerability of any individual dose of study product should be based on an assessment of acute symptoms occurring in close temporal succession to dosing.

In general, the severity of allergic symptoms elicited at a particular dose of study product will define the tolerability of that dose of study product. The place where there is the greatest need for clinical judgment in determining the tolerability of a dose is when the dose elicits mild allergic symptoms. [Table 5](#) illustrates the likely combinations of symptom severity and tolerability.

Table 5: Allergy Symptom Severity and Study Product Dose Tolerability

Symptom Severity	Assessed Tolerability
None	Tolerated
Mild, oropharyngeal symptoms only	Tolerated
Mild, meeting pre-defined tolerability criteria (Section 6.5.1)	Tolerated
Mild, not meeting pre-defined tolerability criteria (Section 6.5.1)	Not tolerated
Moderate (except for rare exceptions, Section 6.5.1)	Not tolerated
Severe	Not tolerated

In general, the severity of an allergic reaction will correspond to the maximum severity of any of its symptoms.

No symptoms: If a dose elicits no symptoms, the dose will be assessed as tolerated.

Mild symptoms: When dosing with study product elicits an acute reaction characterized by the appearance of only a mild symptom or symptoms, the investigator will be required to assess whether the dose was or was not tolerated. The determination of tolerability must be made based on clinical judgment. The following are presented as guidelines for determining whether a dose associated with the emergence of a mild symptom or symptoms was tolerated. A dose eliciting only mild symptoms may be considered to be tolerated if the symptoms:

- Are isolated to a single organ system
- Resolve with no pharmaceutical intervention or with a single oral administration of an H1 antihistamine
- Do not require administration of epinephrine
- Are not worsening in intensity or distribution over time
- Resolve, or shows definite signs of resolving, in under 1 hour
- Do not include objective wheezing

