Based on experience from Phase 2, most acute allergic responses to dosing that are characterized by mild symptoms would be anticipated to meet the above criteria. If, however, an allergic response to dosing is characterized by mild symptoms that do not meet all of the above criteria (eg, has mild symptoms occurring in 2 or more organ systems, requires treatment with 2 doses of antihistamine or 1 dose epinephrine, shows progression in severity or distribution over time, is protracted in duration, or includes objective wheezing), then even though the allergic symptoms may be mild, the dose should be assessed to be not tolerated. If a dose elicits mild symptoms that do not fit all of the above criteria and the dose is assessed to be tolerated, then a brief explanation as to why the dose was considered tolerated must be recorded in the CRF.

Moderate symptoms: In general, if a dose elicits moderate symptoms, the dose will be assessed as not tolerated. There may, however, be rare occasions when a dose eliciting moderate symptoms could be assessed as tolerated. Generally, this would only be the case for a transient, self-limited (requiring no intervention and resolving completely) symptom occurring in a single organ system. In addition, typically the symptom would be subjective only. Any dose associated with moderate symptoms and assessed as tolerated must be accompanied by a brief explanation in the CRF as to why the dose was considered tolerated.

Severe symptoms: If a dose elicits severe symptoms, the dose will be assessed as not tolerated. Whenever a dose elicits an allergic response characterized by 1 or more severe symptoms, the crucial decision, after adequate treatment for the allergic reaction has been administered, will be to determine whether the subject should continue in the study, dosing at a reduced dose level, or be discontinued early from the study. Please refer to individual stopping rules in [Section 7.8.2](#).

The determination of tolerability will decide the course of action to be taken in response to dose-related reactions ([Section 6.5.3](#)).

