- In general, if a subject requires only 1 or 2 doses of an antihistamine to treat mild symptoms occurring during the course of the initial escalation, then the initial escalation may continue. If, however, the subject requires a second medication (eg, epinephrine or a beta-agonist) to treat the symptoms, or more than 2 doses of an antihistamine, the initial escalation is to be terminated and the subject is to receive no further OIT, even if the symptoms were assessed to be mild. Use of epinephrine to treat dose-related symptoms, even in the unlikely event that the symptoms are graded as mild, will be cause to terminate the initial escalation.
- **Moderate symptoms:** For *moderate symptoms*, if the symptoms are not worsening or amassing at a rapid pace, then a stepwise approach to treatment may be taken at the discretion of the investigator.
 - If the first action undertaken is to implement an observation period, the observation period should not exceed 30 minutes before either the symptoms are noted to be resolving or therapy is instituted.
 - Whether treatment is initiated immediately or after an observation period, the subject may be treated first with antihistamines or immediately with epinephrine, as deemed appropriate by the investigator.
 - Other therapies may be added either sequentially or simultaneously, per investigator judgment. If moderate symptoms occur at any of the doses below 6 mg (ie, up to and including 3 mg), then the desensitization procedure will be discontinued and the subject considered an escalation failure and desensitization nonresponder.
 - The decision to discontinue escalation is to be based solely on the determination of whether the allergic reaction was of moderate severity.
 - Although it is generally the case that some form of treatment will be instituted for moderate symptoms, treatment is not a requirement for assessing an allergic reaction as being of moderate severity.
- **Severe symptoms:** For *severe symptoms*, the actions taken should be to discontinue the initial escalation and administer the appropriate rescue medications. The desensitization procedure will be discontinued regardless of the dose at which the severe symptom or symptoms occurred, and the subject will be considered an escalation failure and desensitization nonresponder.

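### The Table 1 Day 2 note sends every Group 1 subject with mild symptoms at the confirmatory 3 mg dose to home dosing, including those whose dose was judged not tolerated and whom Sections 3.1.1 and 6.3.2 stop

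*Protocol*

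**What the plan says.** Group 1 subjects who tolerate at least 3 mg on Day 1 return on Day 2 for one confirmatory 3 mg dose. The Protocol states two rules for what follows.

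**By severity.** The notes under Table 1 (Section 3.1.1), repeated under the Initial Escalation Schedule in the Synopsis, read: "Subjects with either no symptoms or mild symptoms on Day 2 at 3 mg will start daily home dosing at 3 mg" on Day 3. The companion note reads: "Subjects with moderate or severe symptoms at 3 mg on either Day 1 or Day 2 will be considered escalation failures".

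**By tolerability.** The text of 3.1.1 above the table reads: "Subjects who do not tolerate this confirmatory dose will be discontinued". The Synopsis (Study Procedures) says the same. Section 6.3.2 has a stop rule, "If dose-limiting symptoms occur on Day 2, there will be no further dosing of AR101", and a go rule, "Those subjects who tolerate the single 3 mg dose of study product on Day 2 will be dispensed a 2-week supply of study product".

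**What tolerated means.** Section 6.5.2 lists conditions under which a dose causing only mild symptoms may count as tolerated. One is that the symptoms "Do not require administration of epinephrine". If the conditions are not all met, "then even though the allergic symptoms may be mild, the dose should be assessed to be not tolerated". An investigator who nevertheless calls such a dose tolerated must record the reason in the CRF. Section 6.5.4 adds that using epinephrine for dose-related symptoms, "even in the unlikely event that the symptoms are graded as mild, will be cause to terminate the initial escalation".

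**The concern.** Mild and tolerated are different categories in this protocol, and Table 5 gives mild-but-not-tolerated its own row. The Day 2 note ignores that row. A subject with a mild reaction in two organ systems, or one treated with epinephrine, meets the note's condition for home dosing and also meets the conditions for being stopped.

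The companion note does not close the gap, because it names only moderate or severe symptoms as failure. Read together, the two notes look like a complete severity-based rule. They are also what a site is likely to consult at the point of dosing, since they sit beside the dose schedule in both the Synopsis and Section 3.

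At stake is who goes from one supervised dose to unsupervised daily dosing the next day with an allergen dose just judged not tolerated. Table 2 has no level below 3 mg to step down to. Classification also turns on the rule: 6.3.2 makes this subject an escalation failure, while the note makes the same subject an Up-dosing entrant.

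**Working it through.** The plan states no figure on this point, so the check is a comparison of rules followed by simple counts.

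**Step 1. Apply each rule to each Day 2 outcome.**

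| Day 2 outcome at 3 mg | Table 1 and Synopsis notes | 3.1.1 text and 6.3.2 |
|---|---|---|
| No symptoms | Home dosing | Home dosing |
| Mild, assessed as tolerated | Home dosing | Home dosing |
| Mild, assessed as not tolerated | **Home dosing** | **Stopped** |
| Moderate | Escalation failure | Stopped (6.5.2 allows rare exceptions; 6.5.4 ends escalation for moderate symptoms at any dose up to 3 mg) |
| Severe | Escalation failure | Stopped |

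The rules conflict outright in the third row.

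**Step 2. Look for text that settles the conflict.** Section 6.3 sends readers to the visit subsections for full detail, but it is speaking of the Appendix 1 schedules of events. Neither Table 1 nor the Synopsis is said to yield to the body text. Section 6.3.2 stops for dose-limiting symptoms and does not use the words not tolerated there. Its go rule, however, is limited to subjects who tolerate the dose, so the effect is the same.

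**Step 3. Exposure per affected subject.**
- Table 2, footnote a: the 2-week interval at 3 mg includes Day 2. Home doses = 14 − 1 = 13.
- Section 6.3.2: home dosing starts on Day 3 and runs for 2 weeks. Home doses = 14.
- The only contact that 6.3.2 itself schedules in that time is the Day 3 telephone call.

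**Step 4. Number of subjects.** Section 7.8.3 plans 130 Group 1 subjects. Fewer reach Day 2, because Day 1 failures leave first, so 130 is a ceiling. The documents give no rate of mild, not-tolerated reactions on Day 2. The rates below are assumed:
- 1%: 130 × 0.01 = 1.3
- 3%: 130 × 0.03 = 3.9

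That is about 1 to 4 people if every such subject were handled by the note.

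**Step 5. Effect on the analysis.** SAP Section 3 has no escalation-failure endpoint. The Safety population needs only one dose (SAP 4.1). Food challenge summaries use completers unless otherwise noted (SAP 9.1). Event summaries put initial escalation and up-dosing together for Group 1 (SAP 6.1). Group 1 disposition and exposure would shift for a few subjects, and no planned efficacy or primary safety analysis would change materially.

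**The case against.** The best case for leaving the text alone is that the intent is plain and is stated several times. The sentence stopping subjects who do not tolerate the dose sits directly above Table 1 and again in the Synopsis. Section 6.3.2 governs the visit and controls dispensing, and home dosing cannot start without that supply. The note can be read as shorthand, since 6.5.2 says that severity generally defines tolerability and expects most mild reactions to meet the criteria. Section 6.5.4 already covers the worst cases, including epinephrine.

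There are also backstops. Families are told to call the site after an acute reaction at home (6.5.5.2). A home dose suspected not to have been tolerated brings the subject back for the next scheduled dose under supervision, and mild symptoms on four or more occasions in a week prompt observed dosing (6.5.3.1). Finally, the SAP of July 2019 (Section 2.3) has Group 1 subjects who were on daily dosing staying on it for the rest of the study. This suggests that Initial Escalation was already over.

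Much of this stands as a limit on reach. A careful site would probably follow the body text, so the number affected may be zero. The 13 or 14 doses apply mainly to someone who reports nothing further. A dose the investigator calls tolerated with a recorded reason creates no conflict. The figure in 6.5.4 is labelled Day 1, so that section supports the point without being its basis. If Initial Escalation was complete, an amendment would protect no further subjects, though the documents do not say so outright.

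None of this makes the note correct. It is an unqualified dosing instruction, it appears twice, and it contradicts the section it belongs to.

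**Conclusion.** The concern holds. The Day 2 note is wrong as written for subjects with mild symptoms whose confirmatory dose is assessed as not tolerated: it starts home dosing where 3.1.1 and 6.3.2 end treatment.

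The reach is narrow. It is at most about 1 to 4 subjects under an assumed 1% to 3% rate applied to the ceiling of 130, and possibly none if sites follow the body text. Each could take up to 13 or 14 home doses before the next scheduled observed dose, fewer if further symptoms bring the subject in. The main analyses are not materially affected. The correction should be made because the rule concerns dosing safety and costs almost nothing to repair.

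**What to change.** Change the notes under Table 1 in Section 3.1.1 and under the Initial Escalation Schedule in the Synopsis.

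- Day 2 note: *Subjects with no symptoms, or with mild symptoms assessed as tolerated (Section 6.5.2), on Day 2 at 3 mg begin home dosing at 3 mg/d on Day 3.*
- Failure note: *Subjects who do not tolerate 3 mg on Day 1 or Day 2, including all with moderate or severe symptoms, are escalation failures and are discontinued.*

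This agrees with 6.3.2, with 6.5.2 for mild reactions, and with the rule in 6.5.4 on moderate symptoms at doses up to 3 mg. The cost is two note lines in two places at the next amendment, with a short notice to sites. No new data or visits are needed.

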3.1.2 Up-dosing (Group 1 Only)

Subjects will receive AR101 starting at a dose of 3 mg once daily and gradually escalating every 2 weeks to a maximum of 300 mg once daily, according to the Up-dosing Maintenance

Schedule ([Table 2](#)). All escalation doses will be administered under direct observation; subsequent doses will be dispensed to the subject/guardian and administered at home. Doses may be adjusted for tolerability or intercurrent illness; the Up-dosing period may thereby be extended to a maximum of 40 weeks. Subjects unable to escalate to 300 mg within 40 weeks will be considered escalation failures for analysis purposes. Subjects able to escalate to 300 mg and maintain this dose regimen for 2 weeks will have completed Up-Dosing and will enter the Maintenance Period.

Table 2: Up-dosing Maintenance Schedule (Group 1 Subjects Only)

Up-dosing and Maintenance Schedule (Group 1 only)			
Dose Number	AR101 Dose, mg	Interval (weeks)	Percent Increase from previous dose
1	3	2 ^a	n/a
2	6	2	100
3	12	2	100
4	20	2	67
5	40	2	100
6	80	2	100
7	120	2	50
8	160	2	33
9	200	2	25
10	240	2	20
11	300	2	25

^a Interval includes Day 2 of Initial Escalation.

n/a = not applicable.

3.1.3 Repeat Up-dosing (Subjects Switching to Daily Dosing)

If a subject meets the criteria for switching to AR101 daily dosing and is at a study site that has not yet received approval to enroll these subjects in ARC008, the subject may begin daily dosing and have visits in Repeat Up-dosing in ARC004 until they can enroll in ARC008 ([Section 3](#)). If ARC008 is available, the subjects will complete an Exit/Early Discontinuation visit in ARC004 and enroll in ARC008.

Subjects entering the Repeat Up-dosing Period will start with a daily dose of either 80, 120, or 160 mg at the discretion of the investigator. The dose will be increased every 2 weeks as per [Table 3](#), until the subject reaches the target dose of 300 mg daily.

To escalate to the next dose, subjects must be tolerating the current dose. Some subjects may require de-escalation, and once the lower dose is tolerated they may again attempt to proceed with up-dosing. To allow for a personalized titration of dosing, the Repeat Up-dosing Period will last for a maximum of 26 weeks. Subjects who are not able to achieve the target dose of

300 mg/day and tolerate that dose level within 26 weeks will be discontinued from AR101 dosing and complete an Early Discontinuation Visit; these subjects will not be eligible to participate in ARC008.

Subjects who reach the target maintenance dose of 300 mg and maintain this dose for at least 2 weeks (maximum duration of Repeat Up-dosing of 26 weeks) will exit ARC004 and enter ARC008 when it is available. If ARC008 is not available at the time the subject expects to exit ARC004, subjects will continue daily dosing and have visits in ARC004 until ARC008 is available, then continue dosing in ARC008.

Table 3: Repeat Up-dosing Schedule (Subjects Switching to Daily Dosing)

Repeat Up-dosing Schedule (Subjects Switching to Daily Dosing)	
Investigational Product Dose, mg ^a	Interval (weeks)
80	2
120	2
160	2
200	2
240	2
300	2

^a All mg doses shown refer to milligrams of peanut protein.

3.1.4 Maintenance

Subjects entering the Maintenance Period will continue AR101 300 mg once daily, undergoing directly observed dosing at 12 and 24 weeks. Down-dosing may be necessary during the Maintenance Period due to safety or tolerability reasons, but such subjects will remain in the Maintenance Period even if they are temporarily taking a dose of less than 300 mg. The duration of the Maintenance Period does not reset if this occurs. After approximately 24 weeks of daily AR101 treatment at 300 mg in the Maintenance Period, Group 1 subjects will undergo a Post-Maintenance DBPCFC with a maximum dose of 2000 mg of peanut protein (4043 mg cumulative), according to the DPBCFC Schedule (Table 4). Subjects who do not tolerate \geq 300 mg peanut protein (443 mg cumulative) will be considered treatment failures and will be discontinued. Subjects who tolerate \geq 300 mg peanut protein (443 mg cumulative) will enter the EM and continue taking 300 mg/d of AR101 until the results of the alternate regimens explored in Group 2 subjects are known.

Table 4: DBPCFC Schedule (All Time Points)

DBPCFC Schedule (All Time Points)	
Challenge Dose, mg	Cumulative Dose, mg
3	3
10	13
30	43
100	143
300	443
600	1043
1000	2043
2000	4043

3.1.5 Extended Maintenance

The EM periods will differ between and within the 2 groups in duration and dosing regimen (see below and [Figure 1](#)). However, all EM subjects who complete their dosing regimen, regardless of group or cohort assignment, will have an Exit DBPCFC up to a single highest dose of 2000 mg of peanut protein (4043 mg cumulative).

Group 1

All Group 1 subjects who tolerate ≥ 443 mg cumulative peanut protein in the Post-Maintenance DBPCFC will enter the EM period. Subjects who do not tolerate ≥ 443 mg are not eligible to continue for safety reasons. The EM period for Group 1 subjects will initially consist of QD dosing while the Group 2 cohorts are undergoing evaluation as outlined below. Conditional upon the safety and DBPCFC outcomes assessed in the Group 2 participants, Group 1 subjects may have their dosing interval serially lengthened from QD to QOD, QOD to BIW, BIW to QW, and QW to QOW, as tolerated. The duration of each of these interval extension periods will be adjusted, based on Group 2's experience, from between 8 to 28 weeks, as tolerated. In clinic visits during the EM for Group 1 subjects will continue to occur every 14 weeks. Following the completion of the longest tested dosing interval, Group 1 subjects will then undergo an Exit DBPCFC and ARC004 will conclude.

Group 2

As they enter ARC004, Group 2 subjects will be consecutively assigned to 1 of 3 cohorts and continue to receive AR101 in the following fashion:

- The first 120 Group 2 subjects (ie, 1 to 120) entering ARC004 will form Cohort 1 and continue to receive QD treatment for 28 weeks as tolerated and then undergo an Exit DBPCFC.

- The next 50 Group 2 subjects (ie, 121 to 170) entering ARC004 will form Cohort 2, receiving AR101 300 mg QOD for 4 weeks, and then BIW for 24 weeks, as tolerated, and then undergoing an Exit DBPCFC.
- All remaining Group 2 subjects (ie, 171 to end) entering ARC004 will form Cohort 3. Upon entering Cohort 3, these subjects will be randomized 1:1:1 to receive AR101 in 28 week periods, as follows. Cohort 3A will receive 300 mg QD for 56 weeks as tolerated and then undergo an Exit DBPCFC. Cohort 3B will receive 300 mg QD for 28 weeks and then 300 mg QOD for 4 weeks followed by BIW for 24 weeks, as tolerated, and then undergo an Exit DBPCFC. Cohort 3C will receive 300 mg QD for 28 weeks, 300 mg QOD for 4 weeks followed by BIW for 24 weeks, and then 300 mg QW for 28 weeks, as tolerated, and then undergo an Exit DBPCFC.

Throughout ARC004 EM, the first 2 doses at extended nondaily dosing intervals (BIW, QW, QOW) will always be administered under direct supervision in the clinic; QOD dosing is an exception and can be initiated at home. Thereafter, the doses will be administered at home as tolerated, and recorded in the subject diary. Investigators may, at their discretion, bring subjects back to the research unit for an observed dose at any time. All AR101 doses will be judged by the investigator to be tolerated or not tolerated according to criteria previously established in ARC003 and specified in [Section 6.5.2](#).

Dosing intervals should be as consistent as possible, preferably on the same days each week.

- In the BIW group, doses should be at least 3 days apart (eg. Monday and Thursday each week)
- In the QW group, doses should be taken on the same day (\pm 1 day) each week
- In the QOW group, doses should again be taken on the same day (\pm 2 days), every other week

Any subject receiving nondaily dosing (QOD, BIW, QW, or QOW) who has 1 related SAE; 1 related AE graded severe; 2 related AEs occurring on separate occasions, both graded moderate; or 3 consecutive doses judged “not tolerated,” will be considered a treatment failure in the statistical analysis of each cohort. These subjects will be returned to a 300-mg daily regimen by entering the Repeat Up-dosing period. For the majority of subjects, Repeat Up-dosing will be carried out in Treatment Pathway 2 of ARC008. However, if ARC008 is not available at the study site, subjects may start AR101 daily dosing and have visits in ARC004 until ARC008 is available, then continue dosing in ARC008.

No subject will be exposed to a longer dosing interval if evidence from previous cohorts suggests that doing so would more likely than not cause the subject to either experience more frequent or more severe AEs, or lose desensitization that he or she may have gained/maintained, compared to more frequent dosing. Because subjects in Cohorts 3B and 3C will have had 28 additional weeks of QD maintenance treatment, these subjects will be allowed to proceed to QOD and BIW dosing independent of Cohort 2’s experience according to the judgment of the Safety Monitoring Committee (SMC).

Aimmune will monitor the safety and efficacy in each of the cohorts in accordance with internal procedures and escalate to the internal Safety Monitoring Committee (SMC) for review and recommendation for action. Only when sufficient efficacy and safety evidence is available on a cohort, will the SMC recommend that the next cohort advance to a longer interval between doses. Therefore, only after the safety and efficacy data from Group 2 cohorts are available, reviewed, and approved by the SMC, will the SMC allow the Group 1 patients to modify their once-daily regimen.

For more information on individual-, cohort-, and study-stopping rules, see [Section 7.8](#).

Down-dosing may be necessary during the Extended Maintenance Period due to safety or tolerability reasons; however subjects who had to be down-dosed remain in the Extended Maintenance Period during the dose adjustment. The duration of the Extended Maintenance Period does not reset if this occurs.

Early Discontinuations

Subjects who are discontinued and who do not enter ARC008 will be followed for safety for a minimum of 30 days after the last dose of AR101, 2 weeks after the last food challenge, or until resolution or stabilization of all AEs ongoing at the time dosing is stopped, whichever is longer. In addition, subjects who are discontinued from further AR101 dosing due to chronic or recurrent GI AEs will have experienced an AE of interest (AEI) and will be followed monthly for a minimum of 6 months, or until resolution or stabilization of all GI AEs ([Section 7.3.3.2](#) for more information about GI AEIs).

For subjects who do not tolerate their nondaily dosing regimen and subjects who switch to daily dosing after missing their nondaily dose for > 3 days, the exit DBPCFC will be omitted before discontinuation from ARC004 and enrollment in ARC008.

Subjects who are discontinued will not be replaced.

